8.1.2 Missing items within questionnaires

The scoring of questionnaires with missing items is described in table 2 for the primary outcome (ASQ:SE-2), key secondary outcome (PHQ-9) and SDQ. Justification for the approach taken is also provided in the table.

For other secondary outcomes appropriate guidance does not exist so we will impute up to 25% missing values using the average score of completed items for surveys / time-points where more than 5% of responses have item non-response. Where questions are subdivided into groups this rule will be applied at the group level. Where there are no groupings of survey questions this rule will be applied at the whole survey level.

9 Data manipulations and definitions

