2.2.2 Primary care-giver and co-parent secondary outcomes

Key Secondary Outcome² for primary care-giver and co-parent

- a) Depression – to establish overall effectiveness of the IY programme, using the parent/co-parent report *Patient Health Questionnaire (PHQ-9)*.

Other Secondary outcomes for primary care-giver and co-parent

- b) Carer-child attachment/interaction – measured at 18-month follow-up using parent/co-parent report *Maternal Postnatal Attachment Scale (MPAS)* and/or *Paternal Postnatal Attachment Scale (PPAS)*.
- c) Parenting skill – using parent/co-parent report *Parent Sense of Competence (PSoC)*.
- d) Health Related Quality of Life (HRQoL) – using parent/co-parent report *EQ5D5L*.
- e) Service use – using parent report CSRI.

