9.2 Patient reported outcomes

Table 2: Summary questionnaires and how the scores are calculated

Name	Score range	Description	Interpretation of score
Primary caregiver and co-parent			
PHQ-9	0-27	Measure of depression. 9 item questionnaire, 0-3 for each item	
 - Score 1-04 = minimal depression - Score 5-09 = mild depression - Score 10-14 = moderate depression - Score 15-19 = moderately severe depression - Score 20-27 = severe depression 
Desired direction of effect: decrease
 
Imputation: up to 2 missing values will be imputed using the average score for completed items based on NHS guidance (NHS, no date)

PSoC	0-100	The PSoC contains 17 items developed to assess parenting self-esteem. The measure has two subscales, related to parent satisfaction (e.g., A difficult problem in being a parent is not knowing whether you're doing a good job or a bad one), and	
Scores 70 to 96 = high parental confidence
 
Scores 51 to 69 = moderate parental confidence

		parent self-efficacy (e.g., Being a parent is manageable, and any problems are easily solved). Items are rated on a 6-point scale ranging from strongly agree (1) to strongly disagree (6)	Scores 16 to 50 = low parental confidence Desired direction of effect: increase
EQ-5D-5L	This section of the questionnaire yields a total of 243 theoretically possible health states.	The measure comprises 6 questions. The main EQ-5D-5L health utility is based on questions 1-5 (mobility, self-care, usual activities, pain/discomfort, and anxiety/depression), each of which are scored on a five point scale (1: best response, 5: worst). The final question is a stand-alone item, a 0-10 self-assessed thermometer scale scored in units of 0.1 (0=worst, 10=best).	0 = equivalent to death 1 = full health negative score = state worse than death Desired direction of effect: increase

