	Version																																		
	2 month	6 month	12 month	18 month	24 month																														
Low or no risk: It is below the cut-off. Social-emotional development appears to be on schedule.	0-24	0-29	0-39	0-49	0-49																														
Monitor: It is close to the cut-off. Review behaviours of concern and monitor.	25-34	30-44	40-49	50-64	50-64																														
Refer: It is above the cut-off. Further assessment with a professional may be needed	35+	45+	50+	65+	65+																														

			
Desired direction of effect: decrease
 
Imputation: scores will be calculated for up to 3 missing items using the average score of completed items. In the context of using the measure as a screening tool, the ASQ:SE-2 user guide recommends this method of imputation for 3 missing items, but recommends no imputation for 1 or 2 missing items because it would not take somebody over one of the screening thresholds. (Jane Squires Ph.D., Diane Bricker Ph.D., 2015). Because we are using the measure for a trial of efficacy we will also impute for 1 or 2 missing items.

Peds-QL	Subscale scores range from 0-100	
The PedsQL Infant is a 45-item questionnaire designed for parents with infants aged 13-24 months. The items represent 5 dimensions; physical functioning, physical symptoms, emotional functioning, social functioning and cognitive functioning.
 
Psychosocial Health Summary Score = the sum of the items over the number of items answered in the emotional social and cognitive functioning subscales.
	
High scores indicate better health related quality of life.
 
Desired direction of effect: increase

		
- Physical Health Summary Score = the sum of items over the number of items answered in the physical functioning and physical symptoms scales.
 
- Total score = sum of all the items over the number of items answered on all the scales.
						

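### The missing-item rule for the other secondary questionnaires depends on how many other respondents left gaps, and it wrongly covers EQ-5D-5L

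*SAP*

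**What the plan says.** SAP section 8.1.2 first sets three instruments apart: their missing-item scoring "is described in table 2 for the primary outcome (ASQ:SE-2), key secondary outcome (PHQ-9) and SDQ". Every other secondary questionnaire gets one general rule. Under it, "we will impute up to 25% missing values using the average score of completed items for surveys / time-points where more than 5" per cent of responses have a missing item. Where a questionnaire has item groups the rule works within groups; otherwise, "Where there are no groupings of survey questions this rule will be applied at the whole survey level". Section 8.1.2 does not say what happens to incomplete forms at a survey or visit at or below the 5% mark.

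EQ-5D-5L is listed among the other secondary outcomes in section 2.2.2. Its row in Table 2 (section 9.2) has no missing-item rule of its own. That row says "The main EQ-5D-5L health utility is based on questions 1-5", lists five different health dimensions on five-point scales, and describes the result as a utility anchored at death and full health.

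The PedsQL row of Table 2 has its own arithmetic: "Total score = sum of all the items over the number of items answered on all the scales".

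Section 7.8 analyses PSoC and EQ-5D-5L, collected at all four time points, with the repeated-measures approach of the primary analysis. MPAS/PPAS, PedsQL and SDQ are collected at 18 months only.

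**The concern.** A missing-item rule should depend on how complete the respondent's own form is. Here it depends on a property of the whole sample at that visit. Two identical PSoC forms with one gap can be treated differently because of what other participants did, and for PSoC the two treatments can sit side by side in one longitudinal model.

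For EQ-5D-5L the problem is different in kind. Averaging answered items makes sense when the items measure one thing and the score is their sum or mean. The EQ-5D-5L utility is a value attached to a combination of levels on five separate dimensions. The mean of four of them is not an estimate of the fifth, and it need not be a level that exists.

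At stake are the consistency of PSoC scores across visits, the loss of usable PSoC and MPAS/PPAS scores, and the validity of some EQ-5D-5L utilities.

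**Working it through.** The SAP states no figure to reproduce here, so the check is of what the rule permits.

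**Inputs.** Cap 25%, trigger 5% (section 8.1.2). Items: EQ-5D-5L 5 dimensions; PSoC 17; MPAS factors 9, 5 and 5; PPAS factors 8, 7 and 4; PedsQL 45 (Table 2). Sample 606 (summary table).

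**1. Items that may be imputed**, as the whole part of 0.25 × number of items:
- EQ-5D-5L: 0.25 × 5 = 1.25, so 1 (1/5 = 20%; two would be 40%).
- PSoC, taken as a whole: 0.25 × 17 = 4.25, so 4 (23.5%). Table 2 mentions two subscales but does not list their items, so caps by subscale cannot be worked out.
- MPAS: 2 of 9, 1 of 5, 1 of 5. PPAS: 2 of 8, 1 of 7, 1 of 4.

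**2. Where the trigger flips.** If all 606 forms are returned, 30 incomplete forms are 30/606 = 4.95% (no imputation) and 31 are 31/606 = 5.12% (imputation). One more incomplete form changes the handling of all the others.

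**3. Chance that visits are scored by different rules.** Assume 500 returned forms per visit, the same true rate r of incomplete forms at each visit, and independence between visits. None of these comes from the SAP. The trigger is met at a visit with 26 or more incomplete forms (25/500 is exactly 5%, which is not more than 5%). Let p = P(Binomial(500, r) ≥ 26). The chance that k visits do not all follow the same rule is 1 − p^k − (1 − p)^k.

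| r | p | three follow-ups | all four visits |
|---|---|---|---|
| 3% | 0.005 | 2% | 2% |
| 4% | 0.108 | 29% | 37% |
| 5% | 0.447 | 74% | 87% |
| 6% | 0.800 | 48% | 59% |
| 7% | 0.957 | 12% | 16% |

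Baseline counts as well, because the footnote to Table 8 adjusts for the baseline measure.

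**4. EQ-5D-5L.** With one dimension missing, four integer answers from 1 to 5 remain: 5^4 = 625 patterns. Their mean is a whole level only if the sum is divisible by 4, which holds for 157 patterns. The other 625 − 157 = 468 give a fraction. For example, answers 1, 1, 1, 3 give 6/4 = 1.5, which is not a point on the five-point scale. The SAP states no rounding rule. Even where the mean is whole, it is borrowed from unrelated dimensions.

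**5. PedsQL.** If k of n items are answered with mean m, Table 2 gives m. Filling the n − k gaps with m and averaging over n gives [km + (n − k)m]/n = m. At the same level of application the two methods agree. They differ in the trigger, the cap and the level (group or total). A form with 18 of 45 items missing (40%) gets a total score under Table 2, but that is above the 25% cap in section 8.1.2.

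**The case against.** The strongest reply is that this is narrow and may never matter. Visit-to-visit inconsistency can reach only PSoC and EQ-5D-5L: MPAS/PPAS and PedsQL are collected once, SDQ has its own rule, and the CARE-Index synchrony score is a coder's overall rating. It also needs item non-response near 5%; at true rates of 3% or 7% the table above gives small chances. The rule is set by survey and visit, not by arm, so both arms at a visit are scored alike, and the model has an indicator for each time point. All of this stands. It limits the size of the problem, but it does not supply a reason for the trigger or make item averaging valid for EQ-5D-5L.

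Several stronger readings are tempting, and the SAP does not support them:
- **That up to 5% of forms in each arm are thrown away (5 of 101 controls, 25 of 505 intervention).** Section 8.1.2 does not say what happens at or below 5%. Leaving those forms unscored is the natural reading, but it is an inference. The 5% is not split by arm, and the counts assume full return and that every incomplete form is at least 75% complete.
- **That three quarters of imputed EQ-5D-5L levels would be fractional.** The 468 of 625 weights all answer patterns equally. It shows that the fault is common among possible patterns, not how often it would occur in this sample.
- **That the 0–10 thermometer would be averaged with the dimensions.** The whole-survey wording allows the thought, but Table 2 treats the thermometer as separate and bases the utility on the first five questions.
- **That the treatment contrast is biased.** Nothing in the SAP shows this.
- **That PedsQL has two incompatible scoring methods.** Step 5 shows that the averaging is the same; only the conditions need aligning.

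**Conclusion.** The point holds in limited form. The 5% condition makes the scoring of partly complete PSoC and MPAS/PPAS forms depend on other respondents' gaps. For PSoC it can change the rule between visits if item non-response is close to 5%. How likely that is cannot be settled from the SAP, which gives no rate; under the assumptions stated, the chance over four visits runs from 2% to 87% for true rates between 3% and 7%.

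The EQ-5D-5L defect does not depend on visit-to-visit variation. Wherever the trigger is met, the rule allows one dimension to be replaced by a value that often defines no health state. The PedsQL passages need reconciling.

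Severity is minor. Only other secondary outcomes are affected; the primary outcome (ASQ:SE-2) and the key secondary outcome (PHQ-9) have their own item rules.

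**What to change.** In section 8.1.2:
- Delete the 5% condition. Prorate whenever at least 75% of the items in the scale or subscale are answered, at every visit, and state that the score is otherwise missing.
- Exclude EQ-5D-5L from item averaging. Set the utility to missing if any of the five dimensions is missing, or multiply impute the index.
- State one PedsQL rule, for example the Table 2 calculation with the same 75% minimum, and say whether the minimum applies by dimension or to the total.

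The cost is SAP wording, best settled before the statistician receives unblinded data at database freeze (section 4.3). There is a trade-off: some EQ-5D-5L forms that are 80% complete will lose their utility. The current rule imputes only where more than 5% of forms are incomplete (31 or more of 606 if all are returned), so at such a visit the number could be more than a few. Multiply imputing the index would recover those records without inventing a health state.

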9.1 Primary outcome

9.1.1 Combining ASQ:SE-2 scores

The ASQ:SE-2 is a set of questionnaires with different versions for different age groups. Consequently, different versions are completed at each time point and so scores may be standardised as part of sensitivity analyses. Four version are used in the study:

- ASQ:SE-2 2 month version – used at baseline and FU1 for some participants
- ASQ:SE-2 6 month version – used at FU1
- ASQ:SE-2 12 month version – used at FU2

- ASQ:SE-2 18 month version – used at FU3

To standardise the scores, two methods will be applied.

9.1.1.1 Z scores

For each of the four versions, Z scores will be calculated as follows:

Z score = (raw score - mean) / standard deviation

Control participants will be used to calculate the control population mean and standard deviation.

9.1.1.2 Percentages

For each of the four versions, percentage scores will be calculated as follows:

Percentage = (raw score - minimum possible score) / maximum possible score

9.2 Patient reported outcomes

Table 2: Summary questionnaires and how the scores are calculated

Name	Score range	Description	Interpretation of score
Primary caregiver and co-parent			
PHQ-9	0-27	Measure of depression. 9 item questionnaire, 0-3 for each item	
 - Score 1-04 = minimal depression - Score 5-09 = mild depression - Score 10-14 = moderate depression - Score 15-19 = moderately severe depression - Score 20-27 = severe depression 
Desired direction of effect: decrease
 
Imputation: up to 2 missing values will be imputed using the average score for completed items based on NHS guidance (NHS, no date)

PSoC	0-100	The PSoC contains 17 items developed to assess parenting self-esteem. The measure has two subscales, related to parent satisfaction (e.g., A difficult problem in being a parent is not knowing whether you're doing a good job or a bad one), and	
Scores 70 to 96 = high parental confidence
 
Scores 51 to 69 = moderate parental confidence

		parent self-efficacy (e.g., Being a parent is manageable, and any problems are easily solved). Items are rated on a 6-point scale ranging from strongly agree (1) to strongly disagree (6)	Scores 16 to 50 = low parental confidence Desired direction of effect: increase
EQ-5D-5L	This section of the questionnaire yields a total of 243 theoretically possible health states.	The measure comprises 6 questions. The main EQ-5D-5L health utility is based on questions 1-5 (mobility, self-care, usual activities, pain/discomfort, and anxiety/depression), each of which are scored on a five point scale (1: best response, 5: worst). The final question is a stand-alone item, a 0-10 self-assessed thermometer scale scored in units of 0.1 (0=worst, 10=best).	0 = equivalent to death 1 = full health negative score = state worse than death Desired direction of effect: increase
MPAS	Quality of attachment: Minimum score = 9, Maximum score = 45. Absence of Hostility: Minimum score = 5, Maximum score = 25. Pleasure in interaction: Minimum	The MPAS contains 19 items developed to assess a mother's attachment to their infant during the first year of life. Each item is scored on a 2, 3, 4, or 5 point scale. Items are scored on different scales: 
 - Items 8 and 12 are scored on a 2-point scale - Item 14 is scored on a 3-point scale - Items 4, 5, 6, 7, 10, 15, 16, 17, 18 and 19 are scored on a 4-point scale - Items 1, 2, 3, 9, 11 and 13 are scored on a 5-point scale. To ensure equal weighting of all questions it is recommended that responses should be recoded to represent a score of 1 (low attachment) to 5 (high attachment) for every question: 
 - Item 1 would be scored as 1; 2; 3; 4; 5 - Item 2 would be scored as 1; 2; 3; 4; 5 	
 - Quality of attachment: Low scores indicate poor quality of attachment - Absence of Hostility: Low scores indicate high levels of hostility. - Pleasure in interaction: Low scores indicate a lack of pleasure in interaction. Desired direction of effect: increase

	
score = 5, Maximum score = 25.
	
 - Item 3 would be scored as 1; 2; 3; 4; 5 - Item 4 would be scored as: 1; 2.3; 3.6; 5 - Item 5 would be scored as 1; 2.3; 3.6; 5 - Item 6 would be scored as 1; 2.3; 3.6; 5 - Item 7 would be (reverse) scored as: 5; 3.6; 2.3; 1 - Item 8 would be (reverse) scored as: 5; 1 - Item 9 would be (reverse) scored as: 5; 4; 3; 2; 1 - Item 10 would be (reverse) scored as: 5; 3.6; 2.3; 1 - Item 11 would be (reverse) scored as: 5; 4; 3; 2; 1 - Item 12 would be (reverse) scored as: 5; 1 - Item 13 would be (reverse) scored as: 5; 4; 3; 2; 1 - Item 14 would be (reverse) scored as: 5; 3; 1 - Item 15 would be scored as 1; 2.3; 3.6; 5 - Item 16 would be scored as 1; 2.3; 3.6; 5 - Item 17 would be scored as 1; 2.3; 3.6; 5 - Item 18 would be scored as 1; 2.3; 3.6; 5 - Item 19 would be scored as 1; 2.3; 3.6; 5 
The 19 items can be pooled together to create three factors for analysis (with items in brackets reverse scored):
 
 - Quality of attachment: items 3 4 5 6 (7) (10) (14) 18 19 - Absence of hostility: items 1 2 15 16 17 - Pleasure in interaction: all items reversed (8 9 11 12 13) 	
PPAS	
Patience and Tolerance: Minimum = 8, Maximum = 40.
 
Pleasure in Interaction:
	
The PPAS contains 19 items developed to assess a father's attachment to their infant during the first year of life. Each item is scored on a 2, 3, 4, or 5 point scale. Items are scored on different scales:
 
 - Item 8 is scored on a 2 point scale - Items 13 and 16 are scored on a 3 point scale 	
 - Patience and Tolerance: Low scores are indicative of low levels of patience and tolerance. - Pleasure in Interaction: Low scores are indicative of low levels of pleasure in interaction with the child. - Affection and Pride: Low scores are indicative of low levels of affection and pride towards the child.

	
Minimum = 7, Maximum = 35
 
Affection and Pride:
 
Minimum = 4, Maximum = 20
	
 - Items 6, 7, 9, 11, 15, 17, 18 and 19 are scored on a 4 point scale - Items 1, 2, 3, 4, 5, 10, 12, and 14 are scored on a 5 point scale. 
Items should be coded in the following manner:
 
 - Item 1 would be scored as 1; 2; 3; 4; 5 - Item 2 would be scored as 1; 2; 3; 4; 5 - Item 3 would be scored as 1; 2; 3; 4; 5 - Item 4 would be (reverse) scored as: 5; 4; 3; 2; 1 - Item 5 would be (reverse) scored as 5; 4; 3; 2; 1 - Item 6 would be scored as 1; 2.3; 3.6; 5 - Item 7 would be (reverse) scored as: 5; 3.6; 2.3; 1 - Item 8 would be (reverse) scored as: 5; 1 - Item 9 would be (reverse) scored as: 5; 3.6; 2.3; 1 - Item 10 would be (reverse) scored as: 5; 4; 3; 2; 1 - Item 11 would be (reverse) scored as: 5; 3.6; 2.3; 1 - Item 12 would be (reverse) scored as: 5; 4; 3; 2; 1 - Item 13 would be (reverse) scored as: 5; 3; 1 - Item 14 would be (reverse) scored as: 5; 4; 3; 2; 1 - Item 15 would be (reverse) scored as 5; 3.6; 2.3; 1 - Item 16 would be (reverse) scored as 5; 3; 1 - Item 17 would be scored as 1; 2.3; 3.6; 5 - Item 18 would be scored as 1; 2.3; 3.6; 5 - Item 19 would be scored as 1; 2.3; 3.6; 5 
The 19 items can be pooled together to create three factors for analysis:
 
 - Patience and tolerance = items 2, 1, 6, 19, 11, 17, 13, and 18 - Pleasure in interaction = items 5, 15, 9, 12, 4, 8, and 10 - Affection and pride = items 3, 7, 14, and 16 	
Desired direction of effect: increase

--	--	--	--

--	--	--	--

Child																																			
ASQ-SE-2 2 month ASQ-SE-2 6 month ASQ-SE-2 9 month ASQ-SE-2 18 month	Varies depending on time-point and measure	
The ASQ:SE-2 is a 36-item parent-report based tool for screening children’s social and emotional development during the first five years of life. The master set comprises 9 questionnaires, ranging from 1-72 months covering 9 specific developmental ages; 2, 6, 12, 18, 24, 30, 36, 48, and 60 months. Each questionnaire covers 6 key social and emotional development areas: self-regulation, compliance, adaptive functioning, autonomy, affect, social-communication, and interaction with people
 
The parent answers the questions by responding on a three-point scale (Most of the time / Sometimes / Rarely or Never). Parents are also provided with the option to highlight any questions where they feel there is a concern.
 
Using the questionnaire Z’s are scored 0, V’s are scored 5, X’s are scored 10 and any box checked for concern is scored as a 5. Total scores for each page are then calculated and summed to provide an overall score for the 36 items.
	
Total scores are transferred onto a simple score-grid, which include cut off scores indicating possible problems. If the child score falls within the clinical range (see table) we will inform the health visitor at the final data collection time-point.
 
  
 	Version	
 
 	2 month	6 month	12 month	18 month	24 month	
   
 Low or no risk: It is below the cut-off. Social-emotional development appears to be on schedule.	0-24	0-29	0-39	0-49	0-49	
 
 Monitor: It is close to the cut-off. Review behaviours of concern and monitor.	25-34	30-44	40-49	50-64	50-64	
 
 Refer: It is above the cut-off. Further assessment with a professional may be needed	35+	45+	50+	65+	65+	
  
		Version						2 month	6 month	12 month	18 month	24 month	Low or no risk: It is below the cut-off. Social-emotional development appears to be on schedule.	0-24	0-29	0-39	0-49	0-49	Monitor: It is close to the cut-off. Review behaviours of concern and monitor.	25-34	30-44	40-49	50-64	50-64	Refer: It is above the cut-off. Further assessment with a professional may be needed	35+	45+	50+	65+	65+		
	Version																																		
	2 month	6 month	12 month	18 month	24 month																														
Low or no risk: It is below the cut-off. Social-emotional development appears to be on schedule.	0-24	0-29	0-39	0-49	0-49																														
Monitor: It is close to the cut-off. Review behaviours of concern and monitor.	25-34	30-44	40-49	50-64	50-64																														
Refer: It is above the cut-off. Further assessment with a professional may be needed	35+	45+	50+	65+	65+																														

			
Desired direction of effect: decrease
 
Imputation: scores will be calculated for up to 3 missing items using the average score of completed items. In the context of using the measure as a screening tool, the ASQ:SE-2 user guide recommends this method of imputation for 3 missing items, but recommends no imputation for 1 or 2 missing items because it would not take somebody over one of the screening thresholds. (Jane Squires Ph.D., Diane Bricker Ph.D., 2015). Because we are using the measure for a trial of efficacy we will also impute for 1 or 2 missing items.

Peds-QL	Subscale scores range from 0-100	
The PedsQL Infant is a 45-item questionnaire designed for parents with infants aged 13-24 months. The items represent 5 dimensions; physical functioning, physical symptoms, emotional functioning, social functioning and cognitive functioning.
 
Psychosocial Health Summary Score = the sum of the items over the number of items answered in the emotional social and cognitive functioning subscales.
	
High scores indicate better health related quality of life.
 
Desired direction of effect: increase

		
- Physical Health Summary Score = the sum of items over the number of items answered in the physical functioning and physical symptoms scales.
 
- Total score = sum of all the items over the number of items answered on all the scales.
						
SDQ	Subscale scores range from 0-10 and total difficulties score ranges from 0-40	
The SDQ is a 25-item questionnaire, with an additional impact supplement, developed to assess children’s behaviour and social and emotional functioning. Our analysis will use ‘Total difficulty’ score comprising 4 of the 5 subscales
 
 • Emotional problems • Conduct problems • Hyperactivity • Peer problems 	Subscale	Range of possible scores	Close to average	Slightly raised (slightly lowered)	High (low)	Very high (very low)
			Emotional problems	0-10	0-2	3	4	5-10
			Conduct problems	0-10	0-3	4	5	6-10
			Hyperactivity	0-10	0-5	6	7	8-10
			Peer problems	0-10	0-2	3	4	5-10
			Total difficulties	0-40	0-12	13-15	16-18	19-40

			
Desired direction of effect: varies depending on subscale. An increase is desired for prosocial behaviour. For other measures a decrease is desired - see table above
 
Imputation: up to 2 missing values will be imputed for each of the 4 subscales based on guidance from the developers website (Youth in Mind, 2016). In addition, up to one missing subscale score will be imputed using the average score of the 3 completed subscales, based on guidance from the Department of Health and Ageing, Canberra, Australia (Department of Health and Ageing, Canberra, 2006).

--	--	--	---

